#### In-person visits (Wk 1, 3, and 5)

Participants will be temperature checked with a non-contact thermometer and screened for COVID symptoms. If their temperature is 100.4°F and above or they endorse any of the COVID symptoms, they will be rescheduled and told to get tested for COVID and see their primary care provider. Participants will be administered a breathalyzer by the research assistant (RA) to check BAC. If BAC is > 0, the RA will wait a few minutes and readminister. If BAC is 0, the RA will proceed with the study. If BAC is between .01 and .049, the RA will have the participant wait until it drops to 0. If the participant refuses to wait, the research team will reschedule their appointment and the participant can leave. If BAC is  $\geq .05$ , the participant will be transported to the WRNMMC emergency department to assess alcohol withdrawal. If the participant refuses to go to the emergency department, they will be informed that the research team will be forced to contact the NSA Bethesda police ([contact]) out of concern for their safety. A member of the study team will walk the participants unless by the judgement of the research assistant, the participant is unable to walk unassisted. In this case, we will contact 911 to dispatch a team to evaluate the participant and transport them as needed to the WRNMMC ED.

Female participants will be asked by the physician if they believe there's been a change to their pregnancy status since their last appointment. If they believe there has been a change, they will undergo a pregnancy screen using a pregnancy test kit, administered by the physician. If the screen is positive, they will be told they are no longer eligible to participate. Further, they will be instructed to contact their primary care provider to confirm the results and discuss the risks of alcohol use during pregnancy. The physician will then assess the participant for adverse events with the SAFTEE.

Next, the RA will conduct the pill counts, MADRS interview, then participants will complete the TLFB self-report form. Participants will then complete the computer questionnaires (APT, PACS, DDT, SIAS-6, SPS-6, and GAD-7) and behavioral tasks (Stop Signal, N-back, and Trail Making). These study sessions will take approximately 2 hrs to complete.

- During week 3 only: they will complete the alcohol cue reactivity procedure and alcohol urge questionnaire administered by the RA. These tasks will utilize a virtual reality bar lab (technology and software details in 10.2) to simulate a bar experience. Participants will first be screened to assess if they are safe to complete the task as outlined in the script. If they fail the screening, the RA will move to the next section of the script. If they pass the screening, the RA will show them how to use the headset and controllers and help them put on the headset. The RA will then launch the task for them to complete. The virtual reality scenarios will include bar scenes and other scenes with drinking alcohol. Some sample images are provided in the "VR images" document. Participants will be instructed that if they feel any discomfort during the task, they should remove the headset immediately. In these cases, the RA will move to the next section of the script. These tasks will take about 10 to 30 minutes to complete. Week 3 study session will take approximately 2.5 hrs to complete.

Participants will be asked the treatment questions and referred to mental health resources by the RA. They will then be scheduled for their next study session by the RA.

During weeks 1 and 3 only: Participants will be instructed to go to the Investigational Pharmacy (building 9) immediately after their appointment to pick up their study medication. They will be escorted by the RA if they don't remember how to get there. If a participant misses an appointment, they will also be asked to pick up the medication at week 5.

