Below are brief descriptions of the procedures for each study session (for a detailed description of the study protocol and assessments see "NAC script" and "NAC assessments" attachments, respectively):

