### Interview:

- **SCID-5 AUD:** Semi-structured diagnostic interview for alcohol use disorder. (First, Williams, Karg, & Spitzer, 2015)
- **Physical exam:** completed by a physician who is an associate investigator on the study.

- **Pregnancy screen:** completed by a physician who is an associate investigator on the study. The Quidel QuickVue hCG Urine kit will be used.
- **COVID screen:** Participants will be screened for possible COVID symptoms and exposure.
- **Temperature screen:** Participants will be temperature checked with a non-contact thermometer.
- **Breathalyzer:** at each in-person appointment, we will assess BAC with a breathalyzer in compliance with the Department of Transportation (DOT)/National Highway Traffic Safety Administration (NHTSA).
- **Pill count and diary:** At each clinic visit, pill counts will be derived from returned pill bottles to determine intake and compare with the medication diaries that the participant is asked to fill out. (Lam et al., 2015)
- **Montgomery-Åsberg Depression Rating Scale (MADRS):** 10-item questionnaire assessing depression symptoms. (Williams & Kobak, 2008)
- **Alcohol Cue Reactivity (ACR):** a task in which the participant is exposed to stimuli associated with alcohol (Rohsenow et al., 2000). This task will be conducted with a virtual reality bar lab using the Oculus rift headset (<https://www.oculus.com/rift-s/>) and software from In Virtuo (<http://invirtuo.com/en/>). Please note that the cue reactivity software from In Virtuo is not directly displayed on their website, but is an adaptation of the PTSD bar scenario (<http://invirtuo.com/en/software/software/>).
- **Systematic Assessment for Treatment Emergent Effects (SAFTEE):** The SAFTEE is a systematic assessment of side effects for clinical trials. Participants are first asked about side effects in an open-ended way and then asked specifically about side effects that frequently occur. This measure takes approximately 5-10 minutes to complete. (Johnson, Ait-Daoud, & Roache, 2005)
  - **Note:** For phone sessions, the study staff will not administer the SAFTEE but rather ask the open-ended question, have you experienced any new or worsening side effects? Would you like to speak with the team physician prior to your appointment in one week?

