**14.0 Risks and Benefits**

**14.1 Risks of Harm:**

Identify all research-related risks of harm to which the subject will be exposed for each research procedure or intervention as a result of participation in this study. Consider the risks of breach of confidentiality, psychological, legal, social, and economic risks as well as physical risks. Do not describe risks from standard care procedures; only describe risks from procedures done for research purposes

Side effects of NAC are uncommon and relatively minor. The most frequently reported side effects are nausea, vomiting, and diarrhea. They often occur at identical rates to placebo. Rarely and primarily with intravenous administration, anaphylactic reactions may occur and can consist of rash, pruritus, angioedema, bronchospasm, tachycardia, and blood pressure dysregulation. Finally, given the limited reports on NAC in pregnant and lactating women, it should not be used in this population in the context of research and thus this is an exclusion criteria.

Sources: 1) FDA approved acetylcysteine labels (<https://dailymed.nlm.nih.gov/dailymed/index.cfm>)

Data collection may risk loss of privacy.

There is a risk of alcohol withdrawal.

There are legal risks if the participant enters the base intoxicated and/or the NSAB police are called.

There is a chance that participants could experience side effects such as nausea, motion sickness, eye strain, or seizures while completing the virtual reality-based assessment. Symptoms of virtual reality exposure can persist and become more apparent hours after use. These symptoms may put participants at an increased risk of injury when engaging in normal activities such as driving, operating machinery, or engaging in other demanding activities.

For military personnel, there is a risk that their command could be informed of their intoxication by the emergency department if the participant is transported there for alcohol withdrawal.

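### In the visible text, a pregnancy test at weeks 1, 3 and 5 is required only if the woman believes her status has changed; a missed period then recorded on the SAFTEE triggers no test

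*Combined protocol and SAP*

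**What the plan says.** Section 12.6 excludes women who are pregnant or trying to conceive within four months, and section 13.3 asks about both on the phone. Section 10.1 has every woman tested at the baseline physical, before randomisation. Section 10.2 names the kit: "The Quidel QuickVue hCG Urine kit will be used". Section 14.1 gives the reason: "given the limited reports on NAC in pregnant and lactating women, it should not be used in this population in the context of research".

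On treatment, section 10.1 (weeks 1, 3 and 5) states: "Female participants will be asked by the physician if they believe there's been a change to their pregnancy status since their last appointment". The test depends on her answer: "If they believe there has been a change, they will undergo a pregnancy screen using a pregnancy test kit, administered by the physician". The next step is: "The physician will then assess the participant for adverse events with the SAFTEE". After a positive test she is told that she has lost eligibility, and the text adds: "Further, they will be instructed to contact their primary care provider to confirm the results and discuss the risks of alcohol use during pregnancy". Drug collection follows the visit: "During weeks 1 and 3 only: Participants will be instructed to go to the Investigational Pharmacy (building 9) immediately after their appointment". A week 5 collection applies only after a missed appointment.

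Section 16.1 lists missed menses among the SAFTEE items. One late period is Minimal, one absent period is Mild, repeated late or absent periods are Moderate, and complete absence is Severe. The Clinical Follow-up Plan in the same section requires every moderate adverse event to be followed until it resolves or is mild and stable.

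Section 10.1 refers to two attachments, the NAC script and NAC assessments ("for a detailed description of the study protocol and assessments see"). These attachments and the consent pages are not available here.

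**The concern.** The plan regards exposure in pregnancy as something to avoid, and it tests every woman once. After that, the written rule depends on what she believes. The objective sign, a late or absent period, is collected by the same physician at the same visit, but only after the decision to test, and no step returns to that decision. A woman who reports a missed period but does not think she is pregnant meets no written trigger. She can then collect or continue study drug unless the physician chooses to act.

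What is at stake is avoidable exposure in a very small number of women, for a drug where the stated worry is sparse data and not known harm. A secondary point is that no visible text asks the study to seek the outcome of an exposed pregnancy.

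**Working it through.** The plan gives no figure on this point, so there is none to reproduce. The check has a textual part and an arithmetical part.

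**1. What each grade of missed menses requires (section 16.1)**

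| Entry | Required step | Pregnancy test named? |
|---|---|---|
| Minimal or Mild | Yearly IRB report if handled as an expected event; if handled as unexpected, IRB report within 48 hours and physician advice on stopping | No |
| Moderate | As above, plus mandatory follow-up; IRB within 48 hours if an expected event is thought possibly due to drug | No |
| Severe | The same reporting rules, plus unblinding if thought drug-related | No |

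So belief is the only written route to the kit. The thinnest cover is at Minimal and Mild, where a first late or absent period falls.

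**2. Dosing that a positive test could stop in one woman.** The dose is 1500 mg twice daily, or 3 g/day (section 18.2), for 7 weeks.
- Week 1: 6 × 7 = 42 days; 42 × 3 = 126 g
- Week 3: 4 × 7 = 28 days; 28 × 3 = 84 g
- Week 5: 2 × 7 = 14 days; 14 × 3 = 42 g

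**3. Which conceptions the trigger can reach.** Assume that the first missed period and a positive urine test both come L = 2–3 weeks after conception. A visit at week w then reaches conceptions up to week w − L.
- Week 1: up to 1 − L = −1 to −2, so only women who conceived at least 1–2 weeks before baseline. The 126 g applies only to them.
- Week 3: up to 3 − L = 0 to 1, so at most the first treatment week.
- Week 5: up to 5 − L = 2 to 3, so the first 2–3 treatment weeks.

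The share of the treatment period within reach is 2/7 = 29% to 3/7 = 43%. Separately, conceptions in the L weeks before baseline that the baseline test missed are also within reach. They are additional to the treatment-period total.

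**4. Expected numbers.** Assume 10–25 women and a conception risk of 0.1–1.2% per woman per month. Seven weeks = 49/30.4 = 1.61 months.
- All conceptions on treatment: 10 × 1.61 × 0.001 = 0.016 to 25 × 1.61 × 0.012 = 0.48
- Within reach: 0.016 × 2/7 = 0.005 to 0.48 × 3/7 = 0.21
- On NAC, halved for equal allocation (section 11.4): about 0.002 to 0.10
- Before baseline, 2–3 weeks (0.46–0.69 months): 10 × 0.46 × 0.001 = 0.005 to 25 × 0.69 × 0.012 = 0.21, both arms together

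These are upper bounds on the added yield, because some of these women would already be tested on their own belief.

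**5. Kits.** Assume a missed-menses entry at 5–10% of visits.
- With the trigger: 10 × 3 × 0.05 = 1.5 to 25 × 3 × 0.10 = 7.5, about 2–8 kits
- Routine testing of every woman at all three visits: 10 × 3 = 30 to 25 × 3 = 75 kits

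**The case against.** The existing protection is substantial. Pregnancy and intent to conceive are exclusions, every woman is tested at baseline, and a physician asks about pregnancy at three visits. That physician then gives the SAFTEE in person with a kit available, and would very likely test a woman who reports a missed period. SAFTEE grades describe severity; they are not written to direct care for any item. Moderate events carry mandatory follow-up. Medical staff may refer any adverse event to primary care, and the physician may stop the drug. A birth defect is a serious adverse event, reportable within 48 hours of being learned of. The attachments may hold the missing instruction.

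Most of this stands, and it lowers the priority. It does not supply the missing link. Moderate follow-up names no test, and the remaining routes are discretionary or concern reporting. For outcomes, reporting depends on the team learning of the event, and no visible step seeks it out.

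A reader might infer that no provision requires action on missed menses at any grade. The Clinical Follow-up Plan does not support that, since it requires follow-up of Moderate entries. A reader might also infer that testing is blocked; nothing in the text blocks it.

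**Conclusion.** The gap is real in the visible text, and it is minor. The conclusion about the trigger rests on the wording of sections 10.1 and 16.1, on the assumption that the attachments and consent pages add nothing. The size rests on four assumptions that the documents do not supply: the number of women, the conception risk, the lag and the missed-menses rate. On those ranges the trigger reaches at most 29–43% of conceptions during treatment, far below one expected event, plus a similar small number from just before baseline.

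Two larger readings of the size are tempting. One adds the pre-baseline weeks to the reachable window and then sets the sum against conceptions during treatment; those weeks lie outside that total, so the fraction would be inflated. The other treats 126 g as the saving for any woman; it applies only to one who conceived before baseline and tested negative there.

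The documents also do not support reading this as a known hazard of NAC in pregnancy. Nor does the point bear on the trial's results: no endpoint, analysis or sample size changes.

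**What to change.** Add one sentence to the week 1, 3 and 5 procedures in section 10.1: a missed-menses entry of any grade on the SAFTEE leads to the existing urine hCG test before study drug is continued or dispensed, and the physician may exempt women who cannot become pregnant. Clinical handling after a positive result stays with the physician. If the attachments already say this, a cross-reference is enough.

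Optionally, add a second sentence, with matching consent wording, that any pregnancy on study drug is reported to the IRB and its outcome sought with the woman's consent, unless the attachments already cover it.

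The cost is about 2–8 extra kits of the type already named, most of them negative, and a follow-up contact only if a pregnancy occurs. Routine testing at all three visits would need 30–75 kits, so the trigger is the cheaper choice.

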#### Phone calls (Wk 2, 4, and 6)

Participants will be assessed with the adverse event open-ended questions and will complete the TLFB self-report form, then will be scheduled for their next study session. Phone calls will last approximately 30 mins.

#### Final Visit (Wk 7)

Participants will be temperature checked with a non-contact thermometer and screened for COVID symptoms. If their temperature is 100.4°F and above or they endorse any of the COVID symptoms, they will be rescheduled and told to get tested for COVID and see their primary care provider. Participants will be administered a breathalyzer by the research assistant (RA) to check BAC. If BAC is > 0, the RA will wait a few minutes and readminister. If BAC is 0, the RA will proceed with the study. If BAC is between .01 and .049, the RA will have the participant wait until it drops to 0. If the participant refuses to wait, the research team will reschedule their appointment and the participant can leave. If BAC is  $\geq .05$ , the participant will be transported to the WRNMMC emergency department to assess alcohol withdrawal. If the participant refuses to go to the emergency department, they will be informed that the research team will be forced to contact the NSA Bethesda police ([contact]) out of concern for their safety. A member of the study team will walk the participants unless by the judgement of the research assistant, the participant is unable to walk unassisted. In this case, we will contact 911 to dispatch a team to evaluate the participant and transport them as needed to the WRNMMC ED.

The physician will assess the participant for adverse events with the SAFTEE. The RA will conduct the pill counts, MADRS interview, and then participants will complete the TLFB self-report form. Participants will complete the computer questionnaires (APT, PACS, DDT, SIAS-6, SPS-6, GAD-7, and Treatment guess) and behavioral tasks (Stop Signal, N-back, and Trail Making). Participants will be asked the treatment questions and referred to mental health resources by the RA. The final visit will take approximately 2 hrs to complete.

## 10.2 Data Collection:

Describe all the data variables, information to be collected, the source of the data, and how the data will be operationally measured.

### Self-report:

1. **Demographics:** We will ask age, sex, years of education, ethnicity/race, weight, height, marital status, college student status, employment status, and pretax household income. Duration: 2 minutes.
2. **Alcohol, Smoking, and Substance Involvement Screening Test (ASSIST).** A measure of current, recent, and lifetime drug use, which has been modified to remove redundant questions regarding alcohol and smoking. Duration 3 minutes. (Humeniuk, Henry-Edwards, Ali, Poznyak, & Monteiro, 2010).
3. **Alcohol Use Disorder Identification Test (AUDIT).** A 10-item measure of alcohol use and misuse. Duration: 2 minutes. (Saunders, Aasland, Babor, De La Fuente, & Grant, 1993)
4. **Alcohol Purchase Task (APT).** 17 item measure assessing preferences for alcohol at various prices. Duration 3 minutes. (Kaplan et al., 2018)
5. **Penn Alcohol Craving Scale (PACS):** The PACS is a 5-item measure of craving for alcohol over the past week. Each item is rated on a scale from 0 to 6. This self-report form takes approximately 3 minutes to complete. (Flannery, Volpicelli, & Pettinati, 1999)
6. **Delayed Discounting Task (DDT).** This task assesses capacity to delay gratification. Duration: 3 minutes. (Kirby et al., 1999)
7. **Social Interaction Anxiety Scale (SIAS-6) and Social Phobia Scale (SPS-6):** 12-item measure on social anxiety and social phobia. Duration: 3 minutes. (Peters, Sunderland, Andrews, Rapee, & Mattick, 2012)
8. **TLFB alcohol/cigarette/marijuana use.** Asks clients to retrospectively estimate their daily alcohol, cigarette, and marijuana consumption over a time period ranging from 7-30 days (on the first meeting) via a self-report form. Duration: 5 minutes. (Sobell & Sobell, 1996)
9. **E-cigarette questions:** "Have you ever used an electronic nicotine product, even one or two times? Do you now use electronic nicotine products?" Duration: 1 minute. (not specifically based on any preexisting measure).
10. **Hooked On Nicotine Checklist (HONC).** A measure of nicotine use and misuse. Duration: 2 minutes. (Difranza et al., 2002)
11. **Anxiety symptoms:** Generalized Anxiety Disorder Screener (GAD-7). The GAD-7 is a 7-item self-report measure assessing symptoms of generalized anxiety disorder. Respondents use a scale from 0 ('not at all') to 3 ('nearly every day') for each symptom. Duration: 1 minute. (Spitzer, Kroenke, Williams, & Löwe, 2006)
12. **Alcohol urge questionnaire (AUQ):** An 8-item measure of acute craving for alcohol. Duration: 2 minutes. (Bohn, Krahn, & Staehler, 1995)
13. **Mental health services:** We will ask if the participant is currently seeing or has seen in the past 90 days a therapist for a mental health problem and what condition. (screening)
14. **Medications and supplements:** A 2+ item measure on prescription and over the counter medications and supplements. Includes name of medication and reason for use. (<https://www.nimh.nih.gov/funding/clinical-research/clinical-research-toolbox/nimh-clinical-research-toolbox.shtml>)
15. **Treatment guess:** Do you think you received placebo or N-acetylcysteine? (standard treatment knowledge question)
16. **Military Service questions:** A 9-item measure of one's military service. Duration: 2 minutes.

### Interview:

- **SCID-5 AUD:** Semi-structured diagnostic interview for alcohol use disorder. (First, Williams, Karg, & Spitzer, 2015)
- **Physical exam:** completed by a physician who is an associate investigator on the study.

- **Pregnancy screen:** completed by a physician who is an associate investigator on the study. The Quidel QuickVue hCG Urine kit will be used.
- **COVID screen:** Participants will be screened for possible COVID symptoms and exposure.
- **Temperature screen:** Participants will be temperature checked with a non-contact thermometer.
- **Breathalyzer:** at each in-person appointment, we will assess BAC with a breathalyzer in compliance with the Department of Transportation (DOT)/National Highway Traffic Safety Administration (NHTSA).
- **Pill count and diary:** At each clinic visit, pill counts will be derived from returned pill bottles to determine intake and compare with the medication diaries that the participant is asked to fill out. (Lam et al., 2015)
- **Montgomery-Åsberg Depression Rating Scale (MADRS):** 10-item questionnaire assessing depression symptoms. (Williams & Kobak, 2008)
- **Alcohol Cue Reactivity (ACR):** a task in which the participant is exposed to stimuli associated with alcohol (Rohsenow et al., 2000). This task will be conducted with a virtual reality bar lab using the Oculus rift headset (<https://www.oculus.com/rift-s/>) and software from In Virtuo (<http://invirtuo.com/en/>). Please note that the cue reactivity software from In Virtuo is not directly displayed on their website, but is an adaptation of the PTSD bar scenario (<http://invirtuo.com/en/software/software/>).
- **Systematic Assessment for Treatment Emergent Effects (SAFTEE):** The SAFTEE is a systematic assessment of side effects for clinical trials. Participants are first asked about side effects in an open-ended way and then asked specifically about side effects that frequently occur. This measure takes approximately 5-10 minutes to complete. (Johnson, Ait-Daoud, & Roache, 2005)
  - **Note:** For phone sessions, the study staff will not administer the SAFTEE but rather ask the open-ended question, have you experienced any new or worsening side effects? Would you like to speak with the team physician prior to your appointment in one week?
- **Treatment questions:** We will ask if the participant is attending the Intensive Outpatient Program and seeing an individual provider at ATS. If no, we will ask why not to both. We will provide personalized recommendations to participants who answer no to both and their reason is anything other than that they completed their treatment at ATS because they improved.

